2.0 Objectives

Our aim is to evaluate and to compare the above described interventions and their effect on the incidence of PRPs in patients with breast cancer undergoing mastectomy and implant-based immediate breast reconstruction (IBR). The ability to identify, prevent and treat these PRPs can help maximize aesthetic results after breast surgery, improve patient satisfaction with both mastectomy and breast reconstruction, and reduce healthcare cost associated with mastectomy and reconstruction complications.

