4.0 Study Outcomes and Study Measures

We will perform a randomized pilot study comprised of eight groups. All of these groups employ accepted techniques, medications and dressings and therefore are not experimental.

Group 1: Breast skin after mastectomy will be clinically examined by the surgeon to determine if there is adequate blood flow to the skin to allow safe coverage of the breast implant. No dye study, ointment, or vacuum dressing will be applied to the breast after implant placement.

Group 2 - Breast skin after mastectomy will be clinically examined by the surgeon, and nitroglycerin (NTG) cream will be applied to the breast skin after implant placement. This cream does not have systemic effects but may improve blood flow to the remnant breast skin after mastectomy.

Group 3 - Breast skin after mastectomy will be clinically examined by the surgeon, and an incisional vacuum-assisted dressing (iVAC) will be placed over the breast incisions after implant placement, which may improve blood flow to the skin and help wound healing.

Group 4 - Breast skin after mastectomy will be clinically examined by the surgeon, and both NTG cream will be applied to the breast skin and an iVAC will be placed over the incisions after implant placement.

Group 5 - Blood flow to breast skin after mastectomy will be examined using a fluorescent dye study called fluorescent angiography (FA) to determine if there is adequate blood flow to the skin to allow safe coverage of the breast implant. No further intervention will be used after implant placement.

Group 6 - Blood flow to breast skin breast skin will be examined using FA, and NTG cream will be applied to the skin after the implant is placed.

Group 7 - Blood flow to breast skin breast skin will be examined using FA, and an iVAC will be placed over breast skin incisions after the implant is placed.

Group 8 - Blood flow to breast skin breast skin will be examined using FA, and both NTG cream and iVAC will be used as interventions after the implant is placed.

The dosage of indocyanine-green (IC-green) to be used for assessment of mastectomy flaps will be in 10 mg boluses, not to exceed 5 mg/kg.

Nitro-Bid® (nitroglycerin ointment, 2%) at a dose of 45 mg (equal to 7.5 cm on the measuring strip provided with packaging) will be used. The paste will be applied to remnant breast skin after skin closure and surgical dressings placed over top.

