4.1 Primary Outcomes

4.1.1 The primary outcomes will be the following perfusion-related problems:

- Soft tissue ischemia/loss (i.e. partial and full thickness soft tissue defects identified postoperatively in clinic follow up)
- Surgical site infection (i.e. soft tissue cellulitis or abscess identified postoperatively either clinically or with wound culture)
- Delayed wound healing (manifesting as suture dehiscence and opening of an incisional wound)

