4.2 Secondary Outcomes

4.2.1 The secondary outcomes will be the following:

- Rate of operative intervention secondary to perfusion related problems as listed in "Primary Outcomes" above, and surgical outcome with regards to mastectomy flaps
- Rate of prescribing of outpatient antibiotics or admission for inpatient IV antibiotics for treatment of surgical site infection

The Effect of Nitroglycerin Ointment, Fluorescent Angiography, and Incisional NPWT on Mastectomy Skin Flap Perfusion-Related Problems Comprehensive Cancer Center of Wake Forest University (CCCWFU)

PI: [name] IRB #00038262 NCT03716050 Date of Document: 05/07/2019

- Wound care management modalities for treatment of delayed wound healing complications as listed in “Primary Outcomes” above, and wound healing outcomes

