5.0 Treatment Plan

	Pre-Operative Visit	Day of Surgery	Week 1 Postop	Week 2 Postop	Week 3 Postop	Week 4 Postop
Enrollment and informed consent	X					
Clinical assessment to determine whether implant/tissue expander can be placed without compromising perfusion		X				
Clinical photos of surgical site	X	X	X	X	X	X
Data sheet documenting outcome			X	X	X	X

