5.1 Study Related Activities

Potential subjects will be identified by the physician, advanced practice provider, or research coordinator. This individual will discuss the study with the patient and answer any questions or concerns they may have. This will take place in an exam room, hospital room, or by phone depending on whether or not the patient is inpatient or a clinic patient.

Signed informed consent will be obtained from each subject who will be undergoing mastectomy with immediate breast reconstruction using breast implants during a pre-operative appointment in the General Surgery (Breast Oncology) or Plastic Surgery clinic. After the subject has been identified as meeting the inclusion criteria by the clinician or research coordinator, the study coordinator will obtain the signed informed consent. A signed copy of the consent form will be given to the subject. Once the patient has agreed to take part in the study and sign the consent form, pre-operative photos of the breast will be taken. Pregnancy tests performed 15 days apart (prior to surgery) is done as standard of care for all women of childbearing age potentially undergoing this surgery.

Twenty subjects will be randomized to each arm of the study using sealed instructions provided by the study coordinator who will inform the clinician of the arm prior to surgery. The envelopes will be filled prior to the study with envelopes containing a document indicating to which group the patient will be a part of. The envelopes will be sealed and shuffled and then labeled from subject 1 through 160.

Once the subject is randomized to an arm of the study, the operating surgeon will be informed of the arm prior to the surgery. On the day of surgery, the surgeon will decide intraoperatively whether an implant/tissue expander can be safely placed without compromising perfusion of the flap. If the surgeon determines that an implant/tissue expander cannot be safely placed, they will continue to be followed as that indicates a perfusion related problem. At that point, another envelope will be introduced into the pre-made envelopes with that subject’s assigned arm. Pictures will be take pre-

The Effect of Nitroglycerin Ointment, Fluorescent Angiography, and Incisional NPWT on Mastectomy Skin Flap Perfusion-Related Problems Comprehensive Cancer Center of Wake Forest University (CCCWFU)

PI: [name] IRB #00038262 NCT03716050 Date of Document: 05/07/2019

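### Section 5.1 calls inability to place an implant a perfusion-related problem, but no listed outcome counts it and no visible text says whether the subject is in the outcome-rate denominator

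*Combined protocol and SAP*

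**What the plan says.** The aim in section 2.0 is comparative: "Our aim is to evaluate and to compare the above described interventions and their effect on the incidence of PRPs". Perfusion-related problems (PRPs) are therefore the target of the trial.

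Section 5.1 has subjects randomised and the surgeon told the arm before the operation. Whether an implant or expander can be placed is decided during surgery. For subjects in whom it cannot, the section says "they will continue to be followed as that indicates a perfusion related problem". It then says that "another envelope will be introduced into the pre-made envelopes with that" subject's arm.

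The primary outcomes in 4.1.1 are three: tissue loss, infection and delayed healing. Tissue loss is defined as "partial and full thickness soft tissue defects identified postoperatively in clinic follow up". Infection must also be found after surgery, and delayed healing means an incision that opens. Section 8.3.1 repeats the same three. In 4.2.1, operative intervention is tied to the listed primary outcomes, and the remaining phrase, "and surgical outcome with regards to mastectomy flaps", is not defined.

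The schedule in 5.0 has a day-of-surgery item, "Clinical assessment to determine whether implant/tissue expander can be placed without compromising perfusion", but the outcome data sheet is completed only at weeks 1 to 4.

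Section 4.0 describes how adequacy of flow is judged. Groups 1-4 use clinical examination. Groups 5-8 use "fluorescent angiography (FA) to determine if there is adequate blood flow to the skin to allow safe coverage of the breast implant", in the words given for Group 5. The other two interventions come later; for Group 2, "nitroglycerin (NTG) cream will be applied to the breast skin after implant placement".

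**The concern.** The plan names an event as an instance of what it is studying, and then has no outcome in which to record it. Followed as written, the closed list in 4.1.1 and 8.3.1 leaves that event out of the PRP rates. The denominator is open too. Section 8.3.1 gives none for the outcome rates, and 8.3.2 gives one only for attrition.

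Two things are at stake. Section 8.0 uses the per-arm estimates to design a larger trial, so each rate needs one fixed numerator and denominator. Also, the placement decision comes after randomisation, is made by a surgeon who knows the arm, and rests on FA in half the groups. If FA changes how often placement is withheld, leaving the event uncounted or the subject out removes different kinds of patient from the FA and non-FA groups.

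**Working it through.** **The plan's own figures.** For 10 events in 20, the exact (Clopper-Pearson) 95% interval is 27.2% to 72.8%, which is the ±22.8 points in 8.3.1. Exact enumeration of the two-sided pooled Z test at 10% v 40%, 20 per group, alpha 0.20, gives power 0.84713, as tabulated. The point does not rest on an arithmetic error.

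**Is she in the denominator?** The relevant texts, side by side:

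- *Towards keeping her.* Inclusion 3.1.3 speaks of reconstruction as possible, so non-placement is foreseen. Section 5.1 has her followed, and deals separately with subjects who come off study. Under 8.3.2, attrition means not attending the final assessment, so a followed subject who attends is not attrition.
- *Towards leaving her out.* She triggers an extra envelope, the device also used for withdrawn subjects. Section 8.1 wants 20 completers per arm without saying whether she is one of them. Exclusion 3.2.2 rules out mastectomy without immediate reconstruction. More weakly, 5.1 says the trial is not intent-to-treat, but the next sentence there concerns non-compliance.

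**Per-arm illustration.** Take 20 implanted subjects, 2 with a listed event (matching the 10% anticipated in 8.3.1), plus k no-implant subjects without a listed event. The documents give no value for k; 0 to 4 is assumed.

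- Left out: 2/20
- Kept, not counted as an event: 2/(20+k)
- Kept and counted: (2+k)/(20+k)

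| k | Left out | Kept, not counted | Kept and counted |
|---|---|---|---|
| 0 | 10.0% | 10.0% | 10.0% |
| 1 | 10.0% | 9.5% | 14.3% |
| 2 | 10.0% | 9.1% | 18.2% |
| 3 | 10.0% | 8.7% | 21.7% |
| 4 | 10.0% | 8.3% | 25.0% |

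At k = 1 the exact 95% intervals are 1.2-31.7% (2/20), 1.2-30.4% (2/21) and 3.0-36.3% (3/21).

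**FA v no FA, direction only.** Let p be the overall risk if all were implanted, u the no-implant share, and h the risk in flagged flaps if implanted. All values are assumed except p = 0.10, which borrows the anticipated rate and is set equal in both groups.

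- Left out: (p − uh)/(1 − u)
- Counted: u + p − uh

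With h = 0.5 and u = 0.15 (FA) v 0.05 (no FA):

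- Left out: 0.025/0.85 = 2.9% v 0.075/0.95 = 7.9%, a difference of −4.95 points.
- Counted: 0.15 + 0.10 − 0.075 = 17.5% v 0.05 + 0.10 − 0.025 = 12.5%, a difference of +5.0 points.

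With h = 0.3 and u = 0.10 v 0.05, the differences are −1.2 and +3.5 points. With equal u (and equal p and h), both are zero. In the first case the Wald 95% half-widths at 80 v 80 are about 7 points (left out) and 11 points (counted), so neither difference would be distinguishable from zero.

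Keeping her without counting the event does not by itself settle this. The rate is then p − uh + u·r0, where r0 is the flagged subjects' risk without an implant. In the first case r0 = 0.5 gives 10% v 10%. With r0 = 0 it is 2.5% v 7.5%, a difference of −5.0 points, almost the same as leaving her out. The no-implant rate therefore has to be visible in its own right.

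**The case against.** The best reply is that the plan is less open than it looks. The outcome list is closed and appears twice. The PRP phrase in 5.1 gives a reason for continued follow-up and need not define an endpoint. The denominator evidence favours keeping the subject, and the extra envelope may only top up the number implanted. On that reading only 10.0% v 9.5% is in dispute.

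Much of this stands: the balance of the text is towards keeping her. It does not close the point. A label of PRP in a trial of PRP incidence conflicts with a list that cannot record it, and no visible text states the denominator. The schema diagram and the data sheet are not in the text I have, so this is a statement about the visible text.

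A reader might infer three stronger things that the documents do not support.

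- *That the plan drops these subjects.* It does not say so; it only allows it.
- *That the choice of rule would materially change the size of the next trial.* No target effect for that trial is given, and the interval for 2/20 alone (1.2% to 31.7%) is far wider than the 9.5% to 14.3% spread at one no-implant subject.
- *That an FA comparison is biased by a known amount, or that a true FA benefit would be misstated.* No passage names an FA v no-FA contrast; it is inferred from the aim and the 80 v 80 power table. The no-implant rates are invented. Section 4.0 describes FA only as an assessment, with nothing further in Group 5, so it offers no mechanism by which underlying risk would differ if everyone were implanted.

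**Conclusion.** The gap is real and should be fixed. Section 5.1 conflicts with 4.1.1 and 8.3.1 on whether non-placement is a PRP to be counted, and the denominator for these subjects is unstated although the text leans towards inclusion.

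Confidence is high on the wording and low on the consequence. With one no-implant subject in an arm of 20 implanted, the reported rate moves between 9.5% and 14.3%, within heavily overlapping intervals; with none it does not move. Distortion of an FA comparison requires no-implant rates that differ with FA, which the documents neither state nor exclude. The case for acting is that the ambiguity concerns definition, which a larger sample would not remove, and that it bears on the rates the pilot exists to supply.

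**What to change.** 1. In 5.1 and 8.3.1, state that a no-implant subject stays in the denominator of her assigned arm even when an envelope is added.
2. In 4.2.1, add the no-implant rate as its own outcome, reported by arm with a 95% CI. Take it from the day-of-surgery assessment already in 5.0 and give it a field on the data sheet.
3. In 8.3.1, report the three listed outcomes in that population, alongside a composite of any listed outcome or no-implant, which honours the label in 5.1. Fix both definitions before analysis.
4. An implanted-only analysis is optional and should be labelled supporting.

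The cost is a few sentences and one data field. Follow-up and the assessment are already planned, the extra envelopes can stay, and nothing changes in how the placement decision is made. The downside is that nitroglycerin and the vacuum dressing are applied after implant placement, so subjects without an implant may not receive them. That slightly dilutes those estimates (one subject in 21 in the example), and the implanted-only analysis would show by how much. The rule on removing non-compliant subjects is a separate matter.

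### Non-placement of the implant is called a perfusion problem in 5.1 but is not a listed outcome, and it is judged with FA in groups 5-8 and by clinical examination in groups 1-4, so any FA comparison depends on how these women are counted

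*Combined protocol and SAP*

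**What the plan says.** All references are to the combined protocol and SAP.

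- **How perfusion is assessed (4.0).** For group 1: "Breast skin after mastectomy will be clinically examined by the surgeon to determine if there is adequate blood flow to the skin". For group 5 the same question is put to a "fluorescent dye study called fluorescent angiography (FA) to determine if there is adequate blood flow to the skin". Groups 2-4 repeat clinical examination and groups 6-8 repeat FA, without restating the purpose.
- **Who decides (5.1).** "the surgeon will decide intraoperatively whether an implant/tissue expander can be safely placed without compromising perfusion of the flap". Before that, "the operating surgeon will be informed of the arm prior to the surgery".
- **What follows non-placement (5.1).** The protocol says of these women that "they will continue to be followed as that indicates a perfusion related problem". A further envelope for the same arm is then added to the pile.
- **The schedule (5.0)** has one day-of-surgery entry for all arms, "Clinical assessment to determine whether implant/tissue expander can be placed without compromising perfusion", with no mention of FA. The outcome data sheet is scheduled for weeks 1 to 4 only.
- **Primary outcomes (4.1).** There are three: soft tissue ischemia or loss, surgical site infection and delayed wound healing. The first is defined by "partial and full thickness soft tissue defects identified postoperatively in clinic follow up". Non-placement is not among them.
- **Analysis (8.3.1)** names the same three outcomes, reports a rate and 95% interval for each, and has no rule for non-placement. Section 5.1 says the trial is not analysed by intention to treat, and 8.1.1 aims for 20 completed subjects per arm.

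**The concern.** FA is one of the three interventions under study, and it is also the instrument that half the arms use to make the placement decision. The same poorly perfused flap could be recognised on the table in an FA arm and missed in a clinical-examination arm. No criterion for non-placement common to all arms is given.

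The text leaves two ways to handle these women, and each affects the FA contrast:

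- **Counted as a perfusion-related problem, following 5.1.** A more sensitive FA raises the rate in its own arms by detection, whatever happens to the skin later.
- **Not counted, and replaced within the arm.** Section 5.1 keeps these women in follow-up but does not say whether they are among the 20. If they are not, FA has chosen which high-risk flaps leave the FA arms.

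Section 8.0 says the larger trial will be designed from these estimates, so a distorted FA rate would carry into that design.

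**Working it through.** **1. The plan's own figures.** The second table in 8.3.1 gives power 0.90284 for 80 v 80, 10% v 30%, two-sided alpha 0.05, pooled Z test. Exact binomial enumeration of that test gives 0.90284. All nine rows of the two tables reproduce to five decimals. The power calculations are not in question.

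**2. Inputs.** From the documents: an anticipated rate of 10% and combined groups of 80 (8.3.1). Assumed, because the documents give no figures: the proportion withheld, *w*, is 2% by eye and 5% or 10% with FA; the later-problem rate, *r*, among women given an implant is 10% by eye and 5% with FA. That the groups of 80 are 1-4 and 5-8 is inferred from the layout; 8.3.1 does not name them.

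**3. If non-placement is counted.** Combined rate = *w* + (1 − *w*) × *r*.

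| Arm | Withheld | Calculation | Combined rate |
|---|---|---|---|
| By eye | 2% | 0.02 + 0.98 × 0.10 | 11.8% |
| FA | 5% | 0.05 + 0.95 × 0.05 | 9.75% (9.8%) |
| FA | 10% | 0.10 + 0.90 × 0.05 | 14.5% |

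A 5-point gap in later problems shows as about 2 points (11.8 − 9.75 = 2.05) in the first FA case and as 2.7 points the other way in the second. The two combined rates are equal when FA withholds (0.118 − 0.05)/0.95 = 7.2%.

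**4. Against sampling error.** For 14.5% v 11.8% at 80 v 80, SE = √[(0.145 × 0.855 + 0.118 × 0.882)/80] = 0.053. The 95% interval is about ±1.96 × 5.3 = ±10.5 points, roughly four times the 2.7-point gap.

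**5. Illustrative tests on the combined rate** (80 v 80, two-sided 0.05, exact; *w* assumed throughout).

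With later problems at 10% in both halves:

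| Withheld, eye v FA | Chance of declaring FA worse |
|---|---|
| 0% v 0% | 0.024 |
| 2% v 5% | 0.07 |
| 5% v 10% | 0.11 |
| 5% v 15% | 0.31 |

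With later problems at 20% by eye and 10% with FA:

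| Withheld, eye v FA | Power to show FA better |
|---|---|
| 0% v 0% | 0.42 (the plan's own row, 0.42287) |
| 5% v 5% | 0.33 |
| 5% v 10% | 0.12 |
| 5% v 15% | 0.03 |

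**6. If non-placement is not counted and these women are replaced.** Filling 80 places takes 80/(1 − *w*) randomised women, ignoring other dropout: 80/0.98 = 81.6 by eye, 80/0.95 = 84.2 or 80/0.90 = 88.9 with FA. About 2 women fall outside the analysed 80 by eye, against about 4 or 9 with FA, and they are the women whose flaps were judged worst. If they stay in the denominator, this selection does not arise.

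**7. Other contrasts.** NTG and iVAC are each given in two of groups 1-4 and two of groups 5-8, so detection by FA is balanced across them.

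**The case against.** The strongest reply is that the plan contains no combined rate. Sections 4.1 and 8.3.1 list three separate outcomes, none of which is non-placement, and ischemia or loss is defined postoperatively. Steps 3 to 5 therefore describe what follows if the 5.1 sentence is carried into the outcome, not something the plan says it will do. That stands. What remains is that 5.1 calls the event a perfusion related problem, 4.1 and 8.3.1 are silent, and an analyst could follow either.

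Second, changing the placement decision is how FA is meant to work. Problems avoided by withholding an implant are part of its effect, and losing the planned implant may itself be a bad outcome. This also stands, once all randomised women are in the denominator. It does not cover replacing these women out of the 20 per arm.

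Third, every withholding rate is assumed, this is a pilot, and no FA test is specified. All true. They limit what can be said about size, but not the need for a counting rule.

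A reader might infer from the 14.5% v 11.8% example that the trial cannot show whether FA helps, or that a real benefit will appear as harm. The documents do not support either. The reversal needs FA to withhold more than 7.2% against 2% by eye, on a rate the plan does not define, and the gap is small beside the sampling error.

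**Conclusion.** The concern holds as a gap in the analysis rules that is specific to FA. Section 5.1 treats non-placement as a perfusion related problem, 4.1 and 8.3.1 omit it, and the decision rests on different assessments in the two halves of the trial. Counting the event exposes the FA contrast to detection bias; replacing these women out of the analysed 20 exposes it to selection by FA itself. Nothing elsewhere in the documents settles which applies.

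The size cannot be stated, since it rests wholly on assumed non-placement and later-problem rates and on an inferred grouping of 1-4 v 5-8. Differences of a few points between halves in the proportion withheld would move a combined rate by a few points, which 80 v 80 could not distinguish from chance. The harm is mainly to the FA estimates carried into the next trial. The NTG and iVAC contrasts are not affected by this mechanism, although an unblinded surgeon could affect them in other ways.

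**What to change.** Reconcile 4.1, 5.1 and 8.3.1 on whether non-placement is an outcome and whether these women count towards the 20 per arm. Then state in 8.3.1 that, for any FA comparison (groups 5-8 v 1-4):

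1. non-placement is reported by arm as a separate outcome;
2. the listed postoperative outcomes are reported over all randomised women, including those without an implant and those who triggered a replacement envelope;
3. any combined rate is shown only beside these two components and is not used alone to judge FA.

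**Cost.** A placement field for the day of surgery, because the outcome data sheet starts at week 1, and an all-randomised population for this contrast, which departs from the statement in 5.1 that the trial is not intent-to-treat and must be written as an explicit exception. No extra visits are needed, no treatment changes, and the sample size target stays as it is.

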Incisional negative pressure wound therapy will consist of a standard sponge dressing with adhesive drape, either Ioban® 2 (3M™) or KCI-V.A.C.® Drape (KCI®), to continuous suction at 125 mm Hg while the patient is in hospital and not to exceed 4 days.

A physician will see the subjects on a regular weekly basis for up to 30 days once the procedure has been completed. These clinical visits are standard of care and the subject's health and well-being will be monitored rigorously during these visits. If during any of these visits, the physician deems a therapy necessary to prevent impairment/damage and improve well-being, the subject will be treated appropriately.

The Effect of Nitroglycerin Ointment, Fluorescent Angiography, and Incisional NPWT on Mastectomy Skin Flap Perfusion-Related Problems Comprehensive Cancer Center of Wake Forest University (CCCWFU)

PI: [name] IRB #00038262 NCT03716050 Date of Document: 05/07/2019

At no point during this study will the needs of the randomized arm/research take priority over the subject's health and well-being.

Study Risks

Risks of surgery may include bleeding, infection, hematoma/seroma formation, risks of anesthesia, implant/tissue expander failure, extrusion, or tissue necrosis.

Risks with ICGLA may include a potential risk for anaphylaxis/urticarial reaction. Caution must be taken with patients with iodine/iodinated contrast allergy. There have been no studies performed to evaluate carcinogenicity, mutagenicity, or impairment of fertility.

Risks associated with the use of nitroglycerin paste may include dizziness, light-headedness, blurred vision, fainting, increased risk of alcohol toxicity if consumed in conjunction with nitroglycerin use, headaches, severe allergic reactions (rash, hives, itching, difficulty breathing, tightness in chest, swelling of mouth, face, lips, throat or tongue), flushing and red, swollen, blistered or peeling skin.

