operatively, intraoperatively, and at week 1,2,3, and 4 post-operatively. In addition to these pictures, the data collecting sheet will be completed by the physician, advanced practice provider or study coordinator at week 1, 2,3 and 4 post-operatively.

This is not an intent-to-treat trial. In order to ensure that we are able to gather the most information from this study, we want to be able to closely monitor our enrolled subjects and remove any subjects that are non-compliant with their randomized arm. The study coordinator will be responsible for keeping a detailed Excel spreadsheet of the enrolled subjects and their respective arms of the study. If a subject comes off the study prematurely, another envelope will be introduced to the pre-made envelopes with the withdrawn subject's arm – in this way the arms will never be unbalanced.

This study will be monitored by the Cancer Center's Safety and Toxicity Review (STRC) for SAEs and will also be monitored for accrual by the Clinical Research Oversight Committee (CROC) since this is an institutional intervention study. The standard operating procedures for the STRC can be found below in appendix c.

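### Section 5.1 lets people who know the arm score the weekly primary outcomes, so the pilot's rates and arm comparisons may carry scoring bias that a rule on who fills in the sheet would reduce

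*Combined protocol and SAP*

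**What the plan says.** **Who scores.** Section 5.1 (Study Related Activities) states that "the data collecting sheet will be completed by the physician, advanced practice provider or study coordinator" at each of weeks 1 to 4. It does not require that person to be unaware of the arm.

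**Who knows the arm.** Also in 5.1:
- Allocation uses "sealed instructions provided by the study coordinator who will inform the clinician of the arm prior to surgery".
- "The study coordinator will be responsible for keeping a detailed Excel spreadsheet of the enrolled subjects and their respective arms of the study".
- "the operating surgeon will be informed of the arm prior to the surgery".

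The documents do not say whether an advanced practice provider, or a physician other than the operating surgeon, learns the arm.

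**What is scored.** Section 4.1 lists three primary outcomes. Soft tissue ischemia or loss covers partial and full thickness defects found at clinic follow-up. Surgical site infection is "identified postoperatively either clinically or with wound culture", so a culture is not needed. Delayed healing is dehiscence and opening of the incision. None has a threshold for size, severity or duration.

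**What might show the arm.** In section 4.0, fluorescent angiography belongs to the operation, the incisional vacuum dressing runs "while the patient is in hospital and not to exceed 4 days", and nitroglycerin is described only as applied after closure, under the dressings. The 5.0 schedule has "Clinical photos of surgical site" at every visit, including weeks 1 to 4.

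Neither the protocol sections nor section 8 mentions a blinded assessor, coded reading of photographs or adjudication.

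**The concern.** Whether redness is cellulitis, or a shallow skin change is partial-thickness loss, is often a borderline call. A scorer who knows that the patient had no adjunct, or all three, may lean one way without intending to. If the lean differs by arm, it becomes part of each arm's observed rate.

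Section 8.0 says the pilot's estimates will be used to design a larger randomized trial, and 8.3.1 tabulates power for comparing arms of 20 and combined groups of 80. Both uses would take in the bias. Unlike sampling error, it does not shrink as numbers grow. The secondary outcomes on antibiotics and wound care in 4.2 follow partly from the same calls.

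**Working it through.** **1. Overlap between those who may score and those who know the arm (5.1).**

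| Permitted scorer | Knows the arm? |
|---|---|
| Study coordinator | Yes: informs the clinician and keeps the arm list |
| Physician | Yes if the operating surgeon; otherwise not stated |
| Advanced practice provider | Not stated |

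So the text supports *may be scored by someone who knows the arm*.

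**2. The plan's own figures (8.3.1).** Inputs: two-sided pooled-variance Z test; 20 v 20 at alpha 0.20 and 80 v 80 at alpha 0.05; reference rate 10%. For each pair of counts (x, y), z = (x/n − y/n) / √[p̄(1 − p̄)(2/n)] with p̄ = (x + y)/(2n). Power is the sum of the binomial probabilities of all pairs with |z| at or above the critical value. This exact enumeration gives:
- 20 v 20, 10% v 40%: 0.84713 (plan: 0.84713).
- 80 v 80, 10% v 30%: 0.90284 (plan: 0.90284).

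The other seven rows also match. Changing who scores alters none of these inputs, so the sample size and the stated powers stand.

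**3. Illustration of scoring bias.** The documents give no error rate, so the over-call rate c, its direction and its restriction to one side are assumptions. If the true rate is p and the scorer wrongly records an event in a fraction c of uneventful wounds, the observed rate is p + (1 − p)c. With p = 0.10 on both sides:
- c = 0.05: 0.10 + 0.90 × 0.05 = 0.145, so 14.5% v 10%, a false difference of 4.5 points.
- c = 0.10: 0.10 + 0.90 × 0.10 = 0.19, so 19% v 10%, a false difference of 9 points.

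The smallest difference in either power table is 10 points.

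**4. Chance of a significant result when the true rates are equal,** by the same enumeration:

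| Observed rates | 20 v 20, alpha 0.20 | 80 v 80, alpha 0.05 |
|---|---|---|
| 10% v 10% (no bias) | 0.227 | 0.049 |
| 14.5% v 10% | 0.257 | 0.136 |
| 19% v 10% | 0.341 | 0.362 |

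The effect on single-arm comparisons is modest, because those tests are already loose. It is larger for the combined groups. The 80 v 80 column assumes that the bias acts on a whole combined group.

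**5. Could a scorer be unaware at week 1?** Angiography is over at the end of surgery, and the vacuum dressing is off by day 4 at the latest. For nitroglycerin no duration or repeat schedule is given, so its absence at week 1 is an inference.

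**The case against.** The strongest reply is that this is an open-label pilot for estimating rates, that nothing in the plan is contradictory, and that blinded scoring may be harder than it looks.

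Several parts of that stand:
- **Staffing is not documented.** Section 3.1.3 refers to attending plastic surgeons in the plural, but no rota, number of advanced practice providers or rule on access to operative notes is given. The weekly visits are standard-of-care visits at which the physician treats as needed, and that physician may be the operating surgeon.
- **Concealment can fail.** Patients are not said to be blinded and could disclose the arm. The study-risk text in section 4.0 lists skin effects of nitroglycerin and hypersensitivity to the drape, either of which could hint at it.
- **Photographs have limits.** They can show tissue loss and dehiscence but cannot replace an examination or culture for infection.
- **One call is out of reach.** Under 5.1, the decision that an implant cannot be placed counts as a perfusion-related problem. A surgeon who knows the arm makes it, using angiography in those arms.
- **The over-call figures are assumed,** and sampling error is large: 8.3.1 gives about ±22.8 points per arm at a 50% rate.

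These points limit what the fix can achieve. They do not explain why the two roles known to hold the allocation should be free to score. Pilot status does not answer the concern either, since the rates are what the pilot is meant to deliver.

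A reader might go further and infer that all primary outcomes *are* scored by arm-aware staff, that nothing at weeks 1 to 4 could reveal the arm, or that full blinding is available at no cost. The documents support none of these. They are silent on what the advanced practice provider knows, on how long nitroglycerin is used and on staffing.

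**Conclusion.** The concern holds in this form: 5.1 permits the weekly primary-outcome sheet to be completed by the coordinator who keeps the arm list, or by the physician when that is the operating surgeon, and 4.1 leaves tissue loss and infection to clinical judgement. The estimated rates and arm comparisons may therefore be biased.

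The size and direction are unknown. The 4.5-point and 9-point differences show what a one-sided over-call of 5% or 10% would do at a true rate of 10%; they are not estimates of what will happen. The harm would be to planning rates and exploratory comparisons, since this pilot makes no confirmatory claim. It is a gap in design that is cheap to narrow, and it should be narrowed.

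**What to change.** Amend 5.1 as follows:

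1. Among the roles already permitted, the weekly sheet is completed, where available, by an advanced practice provider or non-operating physician who has not been told the arm. The coordinator holding the arm list and the operating surgeon do not complete it when such a person is available.
2. Sheets and photographs are labelled with the subject number only.
3. Every sheet records whether the scorer knew the arm.
4. If no arm-unaware clinician is available, the visit is scored as now and flagged. Coded review of the existing photographs may supplement the scoring of tissue loss and dehiscence, but not of clinically diagnosed infection.

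In 8.3.1, add that primary-outcome rates are reported with and without arm-aware scores, and that intraoperative decisions not to place an implant are reported separately, because they remain unblinded.

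**Cost.** The text change is short, and there is no new visit or procedure, no required new post and no change to sample size or power. The price is a constraint on the clinic rota. Some visits will still be scored by people who know the arm, and patients or skin reactions may unblind others. The flag makes this visible but does not remove it.
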